5.0 Study Procedures

During the initial and therapeutic phases of this study, participants are asked to enter responses daily into a Lully Study app. When the parent sets up the app, they enter their study email address, which is in the format [contact]. The app will send a prompt each morning. The questions the participant is prompted to answer are: Did your child have a bed wetting episode last night? What time was it?

In a free text box the family is asked to add additional information to describe how wet the child was using the following 1-5 scale: 1- wet underwear; 2-wet underwear and damp pajamas; 3-soaked underwear, pajamas; 4-soaked pajamas, damp mattress; 5- soaked mattress

Initial Phase to establish baseline(4 wks)

1. The family will complete a QOL survey, the KIDSCREEN 27 before starting the initial 4 week phase.
2. The family will receive further counseling on behavioral modifications. Handout available for reference in Notes and Attachments.

3. Family will be provided with Malem Enuresis alarm to be used daily during 2 weeks of baseline data collection
4. Family will be asked to complete the KIDSCREEN 27 and the Vancouver questionnaire before starting therapeutic phase

Therapeutic phase

1. Each participant will complete the study phases (S1 and S2) in the order determined by their assigned treatment arm
2. During the 6 weeks of scheduled awakening protocol using Lully Sleep Guardian: each night, a scheduled awakening will be performed with the Lully pod. This will be used to reliably produce a brief awakening by titrating the device to a minimal awakening stimulus during the first night of use. If the brief awakening cannot be produced using the Lully pod, the parent will gently awaken the child
3. The family will complete the KIDSCREEN 27 and the Vancouver questionnaire at the cross-over between the study phases (S1 and S2) and at the completion of their 2 study phase

Study Completion

Family will be asked to return any equipment loaned for the purposes of this study to the Pediatric Urology Clinic at Riley

Compensation

Patient and families will be compensated with \$1 per day for each day they respond to the daily questions prompted by the app about their child's nocturnal enuresis are replied to and an additional \$5 per round of QOL surveys (2 surveys per round). The total will be summed at the conclusion of the study and paid to the participant as an Amazon gift card.

6.0 Reporting of Adverse Events or Unanticipated Problems Involving Risk to Participants or Others

Adverse events will be monitored by the PI and co-investigators. As the participants will be receiving clinical urology care and the interventions are minimal risk, physical adverse events related to the study are not expected. Each event will be handled individually. Adverse events or unanticipated problems involving risk to the participants or others will be reported according to IRB standard operating procedures. If the adverse event represents an unanticipated problem and requires changes to the research protocol or informed consent process/document or other corrective actions in order to protect the safety, welfare, or rights of subjects or others, it will be reported to the IRB using the Prompt Reporting Form within five business days of the investigator becoming aware of the event. Unless determined to not represent an unanticipated problem by HSO staff or the IRB Chair or Chair's designee, the report will be reviewed at a convened IRB meeting for possible action. Any serious unanticipated adverse events will be reported within 24 hours of becoming aware of the event.

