Desmopressin works as a vasopressin analogue to decrease urine production at night (1, 2, 4). It is quicker to improve symptoms compared to alarms once the treatment is discontinued the recurrence of PMNE is significantly higher than alarm devices (2, 4, 6).

The Lully Sleep Guardian was initially developed for use in night terrors. The device works by programing a vibrating disk that is placed under the child's bed to alter sleep patterns and prevent the onset of sleep terrors. The child is not woken up for the treatment of sleep terrors. The device has also be shown to anecdotally improve users' nocturnal enuresis. There have been no reports of safety concerns or hazards with the device (7, 8).

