4.0 Enrollment

Patient Identification, Recruitment, Eligibility Determination

Participants may be recruited from the pediatric urology clinic at Riley Hospital for Children. These patients may be established patients, new patients, or referrals to Pediatric Urology not yet seen in clinic. We will also accept potential participants who are not affiliated with the Pediatric Urology clinic but meet inclusion criteria and have interest. These possible participants include those who attend bedwetting seminars conducted by Pediatric Urology and those who respond to advertising in the community. Potential participants may be recruited from the community through the use of flyers, social media, and INResearch

The initial contact with potential participants may be in person, by phone, or by email. A research team member will provide an overview of the study and be available to answer any questions posed by the family and/or patient. If the family has ongoing interest, they will be asked to complete screening questions to determine if the child meets the eligibility criteria for this study. If a potential participant responds directly to the flyer, they have the option to answer eligibility questions before interaction with a study team member.

To confirm potential participant does not meet any of the exclusion criteria and is eligible, the parent and participant will be asked to together complete two screening questionnaires, the Lully Q &A and the Vancouver questionnaire . Questionnaire results will be reviewed by a study team member and eligibility will be determined.

Consent Procedures

If the candidate is eligible, the informed consent, the assent (if applicable) and the HIPAA authorization will be obtained to enroll the patient. Informed consent and authorization procedures may occur in person or via phone. In either circumstance, the research team member will obtain written signature of consent and authorization. For children 7 – 17 years old, we will obtain child assent in addition to parents informed consent. After consenting, the participant will be immediately assigned to a treatment arm.

Treatment Arms

This study will enroll a total of 40 patients, with 20 in each treatment arm.

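### Section 6 bases its expectation of no physical adverse events partly on urology care that Section 4 does not secure for every child, and no data collection described asks about harm

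*Protocol*

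**What the plan says.** Protocol, Section 6 (adverse events), gives the grounds for not expecting physical events related to the study: "As the participants will be receiving clinical urology care and the interventions are minimal risk". The sentence covers the participants without exception. The section assigns monitoring to the principal investigator and co-investigators. Its limits for reporting to the IRB (five business days, or 24 hours for serious unanticipated events) run from the time of becoming aware. It does not say how that awareness arises.

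Protocol, Section 4 (enrollment), on clinic recruits: "These patients may be established patients, new patients, or referrals to Pediatric Urology not yet seen in clinic". On others: "We will also accept potential participants who are not affiliated with the Pediatric Urology clinic but meet inclusion criteria and have interest". On the channels: "Potential participants may be recruited from the community through the use of flyers, social media, and INResearch". On entry: "Informed consent and authorization procedures may occur in person or via phone".

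Protocol, Section 5 (procedures): the app asks each morning "Did your child have a bed wetting episode last night? What time was it", and a free-text box takes a wetness grade from 1 to 5. The KIDSCREEN 27 and the Vancouver questionnaire are completed before the therapeutic phase, at cross-over and at completion. In the device phase the child is briefly woken each night for six weeks, by the pod or, where that fails, by the parent.

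Protocol, Section 1 (background): no safety concerns have been reported with the device. The use described there is for sleep terrors, in which "The child is not woken up for the treatment of sleep terrors".

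**The concern.** Continuing clinical care is a common way for harm to come to light in a small, low-risk study, and Section 6 leans on it. If some children are not in that care, the premise fails for them and the protocol describes nothing that takes its place. The participants are children aged 5 to 17, and the intervention interrupts sleep every night. Disturbed sleep and daytime tiredness are plausible effects that a family may not think to mention unasked.

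Two things are at stake. Events may be under-counted, and unevenly between clinic and community children. The IRB reporting limits also do not start until someone on the team hears of the event. Section 8 intends a positive result to lead to a comparative trial, so the safety experience here is likely to be carried forward.

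**Working it through.** The protocol states no adverse-event rate or safety sample-size basis, so there is no figure to reproduce. The check is mainly a comparison of sections.

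**Step 1: does the premise cover all participants?**
- Section 6: all participants are taken to be under urology care.
- Section 4: entry is open to established patients, new patients, referrals not yet seen, seminar attendees and responders to community advertising.
- First contact may be by phone or email and consent by phone, so entry requires no clinic visit.
- No section says that unaffiliated children become clinic patients.

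The premise is therefore not secured for unaffiliated children, and it is uncertain for referrals not yet seen.

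**Step 2: is harm asked about elsewhere?**
- Daily app: occurrence and time of wetting. No harm item.
- Free-text box: directed to the wetness grade.
- KIDSCREEN 27 and Vancouver questionnaire: introduced as a quality-of-life survey and as a screening and follow-up questionnaire. Neither is described as recording adverse events, and their content is not in the protocol.
- Visits and interviews: mentioned in Section 9 (privacy) as data sources, but Section 5 schedules none in either phase.

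**Step 3: does the background experience fill the gap?** Only in part. It is described for a use that does not wake the child, whereas Section 5 aims at a brief awakening each night.

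**Step 4: exposure.** 6 weeks x 7 nights = 42 nights per child; 40 children x 42 = 1,680 planned awakenings if every child completes the device phase.

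**Step 5: illustration of what a zero count could mean.** Let *p* be the true proportion of children with an event and *c* the probability that an event reaches the investigators, taken as the same for all children. The protocol gives neither; both are assumptions.
- One-sided 95% upper limit on the reported proportion with 0 of 40: 1 − 0.05^(1/40) = 7.2%. The limit on the true proportion is 7.2%/*c*.
- Chance of no reports when *p* = 10%: (1 − 0.10 × *c*)^40.

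| Assumed *c* | Upper limit on true proportion | Chance of no reports if *p* = 10% |
|---|---|---|
| 1.00 | 7.2% | 1.5% |
| 0.75 | 9.6% | 4.4% |
| 0.50 | 14.4% | 12.9% |
| 0.25 | 28.9% | 36.3% |
| 0.10 | 72.2% | 66.9% |

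The width of the range is the point. Unless families are asked, *c* is unknown, and the data cannot show which row applies.

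**The case against.** The strongest reply has five parts.

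1. *Not affiliated* may describe status at recruitment only, and such a child could still be looked after by the urology team during the study. That reading is possible, but the protocol does not state it. The sections need reconciling whichever reading is meant.

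2. A reader might infer that an event in a community child has no route at all to the investigator. The documents do not support that. Section 9 mentions study visits and interviews, Section 5 has families complete questionnaires and return loaned equipment to the clinic, and any family may report spontaneously. The questionnaires' content is not shown and the consent pages were removed before review, so some capture, or an instruction to report problems, cannot be excluded. What stands is that no described contact is set up to ask.

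3. A reader might also infer that the trial plans to conclude that there were no adverse events, and that its safety data would be worthless. Neither follows. The single aim is effectiveness, no safety endpoint is set, and Section 6 says only that physical events are not expected. Events that are reported would still be informative; it is a low count that would not be reassuring.

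4. The numbers measure a claim that nobody makes. This is fair: the limits are illustration only. The mix of clinic and community children is not stated, the recruitment wording is permissive, and the community share could be small.

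5. Each child passes through both phases, so a stable reporting habit would affect both alike. The exclusions (epilepsy or seizure history, restless leg syndrome, benzodiazepine or clonidine use) and titration to a minimal stimulus also lower the risk. Both points reduce the concern, but neither provides a means of finding events.

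**Conclusion.** The point holds in a limited form. Section 6 rests its expectation partly on a condition that Section 4 does not guarantee, and the data collection described in Section 5 does not ask about harm. Detection over the six weeks of nightly awakenings therefore depends largely on spontaneous report, and few or no recorded events could not be read as evidence of safety. The number of children affected cannot be given, because the community share is not stated. The conclusion assumes that the questionnaires contain no adverse-event item and that no regular contact exists beyond those in Section 5; if either assumption is wrong, the gap narrows. How harm is elicited belongs in the protocol, so an unseen SAP would not settle it. The change should be made, because it is cheap and events not asked about at the time cannot be reliably recovered later.

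**What to change.** 1. Reconcile Section 6 with Section 4 so that urology care is not claimed for all participants. If every child is in fact meant to enter clinic care, say so and say when.

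2. Add one fixed adverse-event question, naming sleep disturbance and daytime sleepiness, to contacts that already exist: a yes/no line in the daily app, or an item in the survey rounds before the therapeutic phase, at cross-over and at completion. Ask it in the same words and at the same times in both phases, so that the behavioral-only phase serves as comparator, and have the investigator review positive answers. An answer before the therapeutic phase would cover a baseline that includes two weeks of alarm use, so it should not be read as a treatment-free reference.

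3. If the visits and interviews in Section 9 are intended as contacts for finding events, schedule them in Section 5.

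The cost is an amended paragraph, one extra question and somewhat more reports to review. The survey version burdens families less but relies on recall over up to six weeks; the daily version avoids that at the price of one more item each morning.

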7.0 Study Withdrawal/Discontinuation

The principal investigator will terminate the involvement of a given participant in the research study if they request to stop participating. The criteria which would result in removal from the study are: participant request to withdraw from the study. The principal investigator reserves the right to withdraw a family from the study if they do not meet the study requirements. Should this occur, the family will be notified by a member of the study team and paid for the activities they completed.

8.0 Statistical Considerations

This study is a simple effectiveness trial to determine if the Lully Sleep Guardian has any effect on benign nocturnal enuresis. If an effect is shown, the research team will use this study to perform a power calculation and facilitate a comparative effectiveness trial comparing Lully Sleep Guardian to current standards of care.

9.0 Privacy/Confidentiality Issues

Research material obtained from living human subjects will include medical records, with medical information collected by the PI/Research Nurse during screening/study visits; and data collected from the questionnaires and interviews.

All paper records containing identifying information will be kept in locked files accessible only to study staff and unlocked only while a study staff member is physically present. All computer records will require password access; computer workstations will be locked whenever a staff person leaves his or her desk.

